**Table 7**

| Timepoint                 | ADA Designations                 | Definition  | Denominator/Evaluable Patients   |
|---------------------------|----------------------------------|---|--|
| Baseline (Day 0 Pre-Dose) | Positive                         | Confirmed positive ADA at baseline                | Number of patients with a baseline and at least one post-baseline ADA assessment |
|                           | Negative                         | Negative ADA at baseline                          |  |
| Post-Baseline             | Positive                         | Confirmed positive ADA at any time after baseline | Number of patients with at least one post-baseline ADA assessment                |
|                           | Negative                         | Negative ADA at all times after baseline          |  |
|                           | Transient Positive iv | (1) Last ADA sampling timepoint is negative       |  |

Sponsor: Boston Pharmaceuticals, Inc.

Protocol Number: BOS161721-02

SAP Version and Date: Version 3.0, 13Nov2020

|                    |                                   |  |   |
|--------------------|-----------------------------------|--|---|
|                    |                                   | 
AND 2a OR 2b:
 
(2a) Only one post-baseline confirmed positive ADA (excluding the last sampling timepoint) exists
 
OR
 
(2b) Two or more post-baseline confirmed positive ADA where the first and last ADA confirmed positive samples are less than 16 weeks apart (irrespective of any negative ADA in between)
  |   |
|                    | Persistent Positive iv | 
1 OR 2 OR 3:
 
(1) Two or more post-baseline confirmed positive ADA where the first and last ADA confirmed positive samples are more than 16 weeks apart (irrespective of any negative ADA in between)
 
OR
 
(2) Confirmed positive ADA at the last post-baseline assessment
 
OR
 
(3) Negative ADA at the last post-baseline assessment and a prior confirmed positive ADA sample occurred less than 16 weeks before the last post-baseline negative ADA sample
 |   |
| Treatment-Emergent | Positive                          | 
A post-baseline confirmed positive result exists with a titer <math>\geq 4</math> times greater than the baseline titer
 
OR
   | Number of patients with at least one post-baseline ADA assessment |

Sponsor: Boston Pharmaceuticals, Inc.

Protocol Number: BOS161721-02

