SAP Version and Date: Version 3.0, 13Nov2020

|  |                                  |  |  |
|--|----------------------------------|--|--|
|  |                                  | 
Any post-baseline confirmed positive result after a negative baseline result
 
Note: The number of treatment-emergent transient positive and treatment-emergent persistent positive ADA will sum to the total positive treatment-emergent ADA
 
Note: If baseline ADA data is missing, the baseline value is treated as negative for this analyses
  |  |
|  | Transient Positive iv | 
Scenario 1:
 
(1) Negative ADA at baseline
 
AND
 
(2) Last ADA sampling timepoint is negative
 
AND (3a OR 3b):
 
(3a) Only one post-baseline confirmed positive ADA (excluding the last sampling timepoint) exists
 
OR
 
(3b) Two or more post-baseline confirmed positive ADA where the first and last ADA confirmed positive samples are less than 16 weeks apart (irrespective of any negative ADA in between)
 
Scenario 2:
 
(1) Confirmed positive ADA at baseline
 
AND
 |  |

Sponsor: Boston Pharmaceuticals, Inc.

Protocol Number: BOS161721-02

SAP Version and Date: Version 3.0, 13Nov2020

|  |                                   |  |  |
|--|-----------------------------------|--|--|
|  |                                   | 
(2) Last ADA sampling timepoint is negative or is the same as baseline ADA levels
 
AND (3a OR 3b):
 
(3a) Only one post-baseline confirmed positive ADA (excluding the last sampling timepoint) exists and the titer at the post-baseline timepoint is <math>\geq 4</math> times greater than the baseline titer
 
OR
 
(3b) Two or more post-baseline confirmed positive ADA where the first and last ADA confirmed positive samples are less than 16 weeks apart (irrespective of any negative ADA in between) and the titers at each of the two or more post-baseline confirmed positive timepoints are <math>\geq 4</math> times greater than the baseline titer
 
Note: If baseline ADA data is missing, the baseline value is treated as negative for this analyses
 |  |
|  | Persistent Positive iv | 
Scenario 1:
 
(1) Negative ADA at baseline
 
AND (2 OR 3 OR 4):
 
(2) Two or more post-baseline confirmed positive ADA where the first and last ADA confirmed positive samples are more than 16 weeks apart (irrespective of any negative ADA in between)
 
OR
   |  |

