|                                 | Negative           | Negative ADA at the post-baseline timepoint   |   |
| Overall                         | Positive           | A patient with positive baseline (pre-dose) ADA or positive post-baseline ADA   | Number of patients with a baseline or post-baseline ADA assessment                    |
|                                 | Negative           | A patient with negative baseline (pre-dose) ADA and negative post-baseline ADA at all time points   |   |

Sponsor: Boston Pharmaceuticals, Inc.  
Protocol Number: BOS161721-02  
SAP Version and Date: Version 3.0, 13Nov2020

[figure not shown]
The frequency and percentages of positive and negative neutralizing antibodies will be summarized in the FAS overall and at each relevant post-baseline timepoint (i.e., Day 15, Day 30, Day 60, Day 90, Day 180, Day 270). The denominators will be the number of patients with non-missing NAb data overall and at each timepoint, respectively.

The adverse event overview table from section 10.1 will be repeated by post-baseline positive and negative ADA as defined in table 7 in the safety analysis set. Additional adverse event analyses may be performed by post-baseline transient positive and persistent positive.

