### 10.1. Adverse Events

AEs will be collected and recorded for each patient from the date of the first dose of study drug until the end of their participation in the study, including the safety follow up period. Severity of adverse events will be graded by the investigator according to National Cancer Institute Common Terminology Criteria for Adverse Events (NCI CTCAE) version 4.03. AEs will also be assessed for relationship to study drug, and seriousness. Adverse events will be marked as AESIs, dose-limiting toxicities (DLTs), or injection site reactions (ISRs), where applicable. AEs will be considered treatment-emergent adverse events (TEAEs) if they started any time after first dose or if the year, month and day of start date were missing. Any missing severity assessments will be assumed to be Grade 3, missing relationship assessments will be assumed to be related, and missing seriousness assessments will be assumed as serious.

Sponsor: Boston Pharmaceuticals, Inc.

Protocol Number: BOS161721-02

SAP Version and Date: Version 3.0, 13Nov2020

An overview of TEAEs will be produced, including counts and percentages of patients with any incidences of TEAE, TEAEs related to study treatment, SAEs, SAEs related to study treatment, any CTCAE grade 2 or higher TEAEs, any CTCAE grade 2 or higher TEAEs related to study treatment, any CTCAE grade 3 TEAEs, any CTCAE grade 3 or higher TEAEs related to study treatment, any CTCAE grade 4 TEAEs, any CTCAE grade 4 or higher TEAEs related to study treatment, TEAEs leading to study treatment discontinuation, treatment related TEAEs leading to study treatment discontinuation, TEAEs of special interest, related TEAEs of special interest, DLTs, related DLTs, TEAEs resulting in death, related TEAEs resulting in death, and injection site reactions. The maximum CTCAE grade (Grades 1-5) will also be included on the summary table.

Adverse events will be coded based on the MedDRA. Patients will be counted once per SOC (and likewise for PT within SOC). TEAEs will be summarized by SOC and PT in descending order of overall incidence of SOC (and PT within SOC). The MedDRA version used is defined in the study data management plan.

Summaries of adverse events by SOC and PT will include the following types:

- TEAEs;
- TEAEs related to study treatment;
- SAEs;
- Related Serious TEAEs;
- CTCAE Grade 3 or higher TEAEs;
- CTCAE Grade 3 or higher TEAEs related to study treatment;
- TEAEs leading to treatment discontinuation; and

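### The adverse-event table by ADA status mixes pre-existing with treatment-emergent antibody and counts events that began before the first positive sample, which biases a descriptive safety comparison

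*SAP*

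**What the plan says.** The current text is SAP v3.0, section 8.3 with Table 7, and section 10.1.

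- **Grouping.** The overview "will be repeated by post-baseline positive and negative ADA as defined in table 7 in the safety analysis set".
- **Post-baseline positive (Table 7).** "Confirmed positive ADA at any time after baseline".
- **Baseline positive (Table 7).** A separate row exists, "Confirmed positive ADA at baseline", so the plan foresees patients with antibody before dosing.
- **Treatment-emergent positive (Table 7).** There are two routes: "A post-baseline confirmed positive result exists with a titer" at least 4 times the baseline titre, or "Any post-baseline confirmed positive result after a negative baseline result". The adverse event table does not use this class.
- **Events counted (10.1).** "AEs will be considered treatment-emergent adverse events (TEAEs) if they started any time after first dose", or if the start date is wholly missing. The overview reports "counts and percentages of patients with any incidences of TEAE".
- **Further work (8.3).** "Additional adverse event analyses may be performed by post-baseline transient positive and persistent positive". This is optional and again rests on post-baseline status.

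**The concern.** A table of adverse events by antibody status is where a reader looks for signs that antibodies formed against the drug bring harm. Injection site reactions and discontinuations due to events are both lines of this overview. Three features blur the comparison:

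1. Antibody that was present before dosing and did not rise is grouped with antibody that arose on treatment.
2. ADA status can change during the study but is treated as fixed. An event on Day 5 in a patient first positive on Day 180 goes in the positive column.
3. A patient has to remain in the study to be sampled and found positive, while the table gives percentages of patients without regard to time at risk.

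The first two tend to hide a real effect, and the third can produce a small difference where there is none.

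**Working it through.** The SAP states no figure for this table, so there is none to reproduce. The definitions were read first and the size then illustrated.

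**1. Where patients fall under the definitions**

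| Patient | Column in planned table | Treatment-emergent under Table 7? |
|---|---|---|
| Baseline positive, later positive, titre unchanged | Positive | No |
| Baseline negative, event Day 5, first positive Day 180 | Positive, event included | Yes, but the event precedes the sample |
| Baseline negative, leaves on Day 40 before antibody would have been detected | Negative | No |

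**2. Equal follow-up, closed form.** Assumptions: background risk p over 270 days at a constant rate, rate multiplied by r after onset, pre-existing antibody harmless. Let L = −ln(1 − p).

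- *Onset uniform over 270 days.* Risk in positives = 1 − e^(−Lr) × (e^(L(r−1)) − 1) / (L(r−1)).
  - p = 0.60, so L = 0.9163.
  - r = 2: 1 − 0.160 × 1.500/0.9163 = 0.738, and 0.738/0.600 = 1.23.
  - With 25% of positives pre-existing: 0.75 × 0.738 + 0.25 × 0.600 = 0.704, ratio 1.17.
  - r = 3: 1 − 0.064 × 5.25/1.8326 = 0.817, ratio 1.36; with 25% pre-existing, 1.27.
- *Scale.* A risk ratio for a common event is compressed anyway. Immediate onset in all positives would give (1 − 0.40²)/0.60 = 1.40 for r = 2 and (1 − 0.40³)/0.60 = 1.56 for r = 3. The loss due to the table is thus 1.40 to 1.23 to 1.17, and 1.56 to 1.36 to 1.27.
- *Onset at Day 90, p = 0.30, r = 2.* L = 0.3567. Cumulative hazard = 0.3567 × (90 + 2 × 180)/270 = 0.594, so risk is 0.448 and the ratio 1.49. With 25% and 50% pre-existing it is 1.37 and 1.25. Treatment-emergent ADA with post-onset events only gives 0.378/0.212 = 1.79.

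Across all 54 such equal-follow-up scenarios the planned ratio was below the one for treatment-emergent ADA with post-onset events.

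**3. With dropout (simulation, 1,000,000 patients per scenario).** Assumptions: 30% ADA positive, uniform onset, p = 0.60. Samples are on Days 15, 30, 60, 90, 180 and 270, which section 8.3 lists for neutralizing antibody and which are assumed here for ADA. Entries are the planned table's risk ratio with no pre-existing antibody / with 25% of positives pre-existing.

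| Dropout by Day 270 | True ratio 1 | 1.2 | 2 | 3 |
|---|---|---|---|---|
| 0% | 1.00 / 1.00 | 1.06 / 1.04 | 1.23 / 1.17 | 1.36 / 1.27 |
| 15% | 1.06 / 1.05 | 1.12 / 1.09 | 1.31 / 1.23 | 1.45 / 1.33 |
| 30% | 1.13 / 1.09 | 1.20 / 1.14 | 1.40 / 1.28 | 1.56 / 1.40 |

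With no effect and no pre-existing antibody, mean follow-up in positives and negatives was about 264 and 246 days at 15% dropout, and about 257 and 223 at 30%. Dividing patient-time at true onset returned the true rate ratio in every cell to within about 0.01.

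**4. Timing of events (simulation, 2,000,000 patients per scenario).** Assumptions: constant-rate onset reaching 20% or 40% by Day 270, dropout of 15% or 25% by Day 210, background risk of 10% or 60%, and no pre-existing antibody.

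- No effect: 58% to 66% of positive patients with an event had their first one before the first positive sample. The spurious risk ratio was 1.07 to 1.17.
- Three-fold effect: the share was 41% to 60%. The table showed about 2.1 to 2.3 for a 10% event and 1.5 to 1.6 for a 60% event.
- For a 10% event with a three-fold effect, about a quarter of first events that truly followed onset fell before the first positive sample.

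**The case against.** The table is descriptive, with no test, causal statement or decision rule, and section 8.3 uses Table 7's post-baseline class consistently. Other planned outputs help. Section 8.3 lists ADA and neutralizing antibody by patient, section 10.1 lists all adverse events, and section 10 presents safety by treatment group by default, so placebo patients who test positive may serve as a reference. All of this stands and limits the weight of the point.

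Precision is also low. Taking 104 active patients (156 × 2/3, from the superseded v2.0) and 20% to 40% ADA, the 90% half-width is about 1.645 × √(0.25/21 + 0.25/83) = 20 points, or 1.645 × √(0.25/42 + 0.25/62) = 16 points. A spurious gap of 4 to 7 points is small beside that.

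A reader might infer four stronger things that the documents do not support.

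- *That a true effect is always diluted.* Longer follow-up in positives pushes the other way. At 30% dropout with no pre-existing antibody, a true ratio of 1.2 appears as 1.20.
- *That the table cannot be read at all.* A three-fold hazard for a 10% event still shows as about 2.1 to 2.3.
- *That most events in positives precede the antibody.* The 58% to 66% share holds only with no effect, and it includes some events after true onset but before detection.
- *That this is the plan's only firm analysis of antibody-related harm.* The v3.0 text examined begins partway through section 7.2.12, and the shells and some other analyses are in separate documents.

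**Conclusion.** The point holds as a bias in one descriptive safety table. Its textual basis is certain: the positive column takes in unboosted pre-existing antibody and events before the first positive sample, and nothing in the table allows for unequal follow-up. The direction is usually toward no difference when antibodies cause events and slightly away from it when they do not.

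The size is not knowable from the SAP. Dilution by pre-existing antibody rests on the assumption that such antibody carries no added risk. The other figures rest on assumed ADA, dropout and event rates, constant hazards, and ADA sampling on the neutralizing antibody days.

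Severity is low. The primary analysis is not affected.

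**What to change.** In section 8.3, present the adverse event overview in three columns:

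1. Treatment-emergent ADA positive, as Table 7 defines it.
2. Baseline positive without the Table 7 titre rise, including any such patient negative afterwards.
3. ADA negative throughout, which matches Table 7's overall negative class.

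Keeping the second group in its own column matters: a plain split into treatment-emergent positive and all others would put those patients in the comparator. Footnote patients with missing baseline ADA, whom Table 7 treats as negative at baseline for the treatment-emergent class.

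For treatment-emergent positives, add a display of events with onset before, and on or after, the first treatment-emergent positive sample. Give rates per patient-time beside the percentages. State that true onset may precede that sample, since the listed days leave gaps of up to 90 days. This split should supplement the overview, not replace it.

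The cost is SAP wording, a revised shell and a comparison of dates the study already collects. The drawbacks are small columns and some misclassification of onset between samples: about a quarter of post-onset first events in the three-fold, 10% scenario.

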## 9. QUALITY OF LIFE

### 9.1. **CCI**

CCI

[figure not shown]
CCI

CCI

CCI

CCI

CCI

CCI

[figure not shown]
9.2. CCI

Sponsor: Boston Pharmaceuticals, Inc.  
Protocol Number: BOS161721-02  
SAP Version and Date: Version 3.0, 13Nov2020

CCI

CCI

CCI

CCI

CCI

## 10. SAFETY

All safety analysis reporting will be based on the Safety Analysis Set. Unless otherwise noted, all safety analyses will be presented overall, by study phase, and treatment group.

### 10.1. Adverse Events

AEs will be collected and recorded for each patient from the date of the first dose of study drug until the end of their participation in the study, including the safety follow up period. Severity of adverse events will be graded by the investigator according to National Cancer Institute Common Terminology Criteria for Adverse Events (NCI CTCAE) version 4.03. AEs will also be assessed for relationship to study drug, and seriousness. Adverse events will be marked as AESIs, dose-limiting toxicities (DLTs), or injection site reactions (ISRs), where applicable. AEs will be considered treatment-emergent adverse events (TEAEs) if they started any time after first dose or if the year, month and day of start date were missing. Any missing severity assessments will be assumed to be Grade 3, missing relationship assessments will be assumed to be related, and missing seriousness assessments will be assumed as serious.

Sponsor: Boston Pharmaceuticals, Inc.

Protocol Number: BOS161721-02

SAP Version and Date: Version 3.0, 13Nov2020

An overview of TEAEs will be produced, including counts and percentages of patients with any incidences of TEAE, TEAEs related to study treatment, SAEs, SAEs related to study treatment, any CTCAE grade 2 or higher TEAEs, any CTCAE grade 2 or higher TEAEs related to study treatment, any CTCAE grade 3 TEAEs, any CTCAE grade 3 or higher TEAEs related to study treatment, any CTCAE grade 4 TEAEs, any CTCAE grade 4 or higher TEAEs related to study treatment, TEAEs leading to study treatment discontinuation, treatment related TEAEs leading to study treatment discontinuation, TEAEs of special interest, related TEAEs of special interest, DLTs, related DLTs, TEAEs resulting in death, related TEAEs resulting in death, and injection site reactions. The maximum CTCAE grade (Grades 1-5) will also be included on the summary table.

Adverse events will be coded based on the MedDRA. Patients will be counted once per SOC (and likewise for PT within SOC). TEAEs will be summarized by SOC and PT in descending order of overall incidence of SOC (and PT within SOC). The MedDRA version used is defined in the study data management plan.

Summaries of adverse events by SOC and PT will include the following types:

- TEAEs;
- TEAEs related to study treatment;
- SAEs;
- Related Serious TEAEs;
- CTCAE Grade 3 or higher TEAEs;
- CTCAE Grade 3 or higher TEAEs related to study treatment;
- TEAEs leading to treatment discontinuation; and
- Dose-Limiting Toxicities
- TEAEs of Special Interest

A summary of TEAEs by SOC, PT, and maximum CTCAE grade will also be prepared. For these summaries, TEAEs will be sorted for each patient by SOC/PT and CTCAE grade; patients will be counted once within a SOC/PT based on their maximum CTCAE grade. Missing CTCAE grade will be counted as grade 3 and will also be presented in a 'Missing' row for completeness.

A summary of TEAEs by PT and maximum CTCAE grade will also be prepared with sections for any TEAE and TEAEs related to study treatment. For these summaries, patients will be counted once within a PT based on their maximum CTCAE grade. Missing CTCAE grade will be counted as grade 3. An additional summary of TEAEs by PT and maximum CTCAE grade will be summarized for all TEAEs and TEAEs related to treatment for PTs with at least one patient experiencing a CTCAE grade 3 or higher and PTs where 10% or more of patients experience a CTCAE grade 1 or 2 for that PT. The summary will be sorted by the total incidence of the PT in the any TEAE section.

A comprehensive listing of all AEs will be provided in a by-patient data listing for the safety analysis set. In addition, the following listings will be provided for the safety analysis set:

Sponsor: Boston Pharmaceuticals, Inc.  
Protocol Number: BOS161721-02  
SAP Version and Date: Version 3.0, 13Nov2020

- TEAEs related to study treatment;
- SAEs;
- TEAEs leading to treatment discontinuation; and
- AESIs
- CTCAE Grade 3 or Higher TEAEs

## 10.2. Clinical Laboratory Evaluations

Laboratory tests will be performed at times defined in the protocol Schedule of Assessments. Clinical chemistry and hematology parameters will be reported based on the International System of Units (SI). The following laboratory evaluations will be reported in data summaries, with asterisks indicating those that will be graded using NCI CTCAE. Grading will be performed by the Central Lab for relevant laboratory parameters based on the details provided in Appendix 13.11. If a grade is not present in the central lab database for a graded lab parameter, the grade will be analyzed as grade 0.

Hematology: Hemoglobin\*, Hematocrit, RBC count, RDW, MCV, MCH, MCHC, Platelet count\*, WBC count\*, CD4+ count\*, Total neutrophils (Abs)\*, Eosinophils (Abs), Monocytes (Abs), Basophils (Abs), Lymphocytes (Abs)\*

Clinical chemistry: Alanine Aminotransferase\*, Albumin\*, Alkaline Phosphatase\*, Aspartate Aminotransferase\*, Bicarbonate, Bilirubin\*, Blood urea nitrogen, C Reactive Protein, Calcium, Chloride, Creatine Kinase\*, Creatinine\*, Glucose (fasting)\*, Glucose (random)\*, Potassium\*, Protein, Sodium\*, Uric acid\*, eGFR (Cockcroft-Gault)\*, eGFR (MDRD)\*, Total cholesterol (fasting)\*, LDL-C (fasting), HDL-C (fasting), Triglycerides (fasting)\*, Gamma Glutamyl Transferase\*.

Coagulation: Prothrombin Intl. Normalized Ratio\*, Activated Partial Thromboplastin Time\*

Urinalysis: pH, Glucose (qual), Protein (qual)\*, Blood (qual)\*, Ketones (qual), Nitrites (qual), Leukocyte esterase (qual), Urobilinogen (qual), Urine bilirubin (qual), Microscopy

Observed values, changes, and percentage changes from baseline for hematology, clinical chemistry, and coagulation laboratory evaluations will be summarized at each visit and most extreme change. Endpoint analyses will be based on changes from baseline assessments at Days 120 and 210.

The number and percent of patients with a CTCAE toxicity grade of 3 or higher will be tabulated by laboratory evaluation with defined CTCAE grading at each visit for hematology, clinical chemistry, coagulation, and urinalysis (protein only). Patients with missing values post-baseline will be excluded from the summary. The denominator for percentages will be the number of patients with a post-baseline assessment for the laboratory parameter in question at that visit.

Hematology, clinical chemistry, coagulation, and urinalysis (protein only) shift tables displaying the shift from baseline to the worst value of CTCAE grade will be presented based on the most

extreme change as it relates to the relevant CTCAE definition. CTCAE relating to “high/hyper” conditions will depend on the maximum post-baseline value while CTCAE “low/hypo” will be reported based on the minimum post-baseline value. Separate shift tables will be prepared for parameters with bi-directional toxicity grading. Lab parameters which are optional, such as gamma glutamyl transferase, will not be included in the shift tables.

Hematology and clinical chemistry laboratory data which is not graded will also be summarized in shift tables of baseline to each visit and most extreme change based on range categories of low (below lower limit of normal [LLN], normal, and high [above upper limit of normal [ULN]]).

Urinalysis laboratory data (excluding protein) will also be summarized in a shift table of baseline to each visit based on range categories of low (below lower limit of normal [LLN]), normal, abnormal, and high (above upper limit of normal [ULN]).

Selected hematology and clinical chemistry laboratory results will be plotted over time for treatment group for MAD phase 1b portion of the study in the safety analysis set. The mean and SD of the change from baseline for selected hematology and clinical chemistry laboratory results will be plotted over time for the POC Phase 2 portion of the study in the safety analysis set.

All laboratory parameters as well as a summary of central laboratory tests and chest x-ray will be provided in patient data listings for all randomized patients. By patient listings of clinical chemistry and hematology data will be presented in the safety analysis set for the DMC and interim analysis only.

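### The by-visit table of CTCAE grade 3 or higher includes urine protein, but the only urine protein test listed for reporting cannot be graded above Grade II

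*SAP*

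**What the plan says.** All of this is in SAP v3.0, section 10.2 and Appendix 13.11.

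- **What is reported.** Section 10.2 introduces its parameter list so: "The following laboratory evaluations will be reported in data summaries, with asterisks indicating those that will be graded using NCI CTCAE". The urine entry begins "Urinalysis: pH, Glucose (qual), Protein (qual", and protein carries the asterisk. Neither 24-hour urine protein nor a protein/creatinine ratio is in the list.
- **Who grades.** "Grading will be performed by the Central Lab for relevant laboratory parameters based on the details provided in Appendix 13.11".
- **Ungraded results.** "If a grade is not present in the central lab database for a graded lab parameter, the grade will be analyzed as grade 0".
- **The table at issue.** Patients at CTCAE grade 3 or higher are to be "tabulated by laboratory evaluation with defined CTCAE grading at each visit for hematology, clinical chemistry, coagulation, and urinalysis (protein only". The denominator is patients with a value for that parameter at that visit.
- **The other displays in section 10.2.** By-visit observed values and changes cover hematology, chemistry and coagulation only. The shift table from baseline to worst CTCAE grade includes urine protein. The by-visit urinalysis shift table leaves protein out. All laboratory parameters go into patient listings.

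**The concern.** The threshold of the table and the scale of the test do not meet. A patient whose urine protein goes from negative to +++ is counted in this row exactly as one who stays negative.

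A zero that is fixed by the rule would sit beside zeros for other parameters that could have come out otherwise, and nothing in the table would tell the reader which is which. In lupus this is an awkward place for it, since the plan's own instruments treat proteinuria as disease activity: it carries a weight of 4 in the SLEDAI-2K form and appears among the BILAG renal items.

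Versions 1.0 and 2.0 of the SAP kept this table to hematology, chemistry and coagulation. Urine protein is an addition in v3.0, and for a qualitative result the addition returns nothing.

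**Working it through.** The plan gives no figure of its own on this point, so there is nothing to reproduce. The check sets the two places side by side.

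**Step 1. Urine protein rows in Appendix 13.11.**

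| Measure | Grade I | Grade II | Grade III | Grade IV | Listed in section 10.2? |
|---|---|---|---|---|---|
| Qualitative protein | + | ++ or +++ (18 years and over) | none | none | Yes |
| 24-hour protein, mg/24h | < 1000 | 1000 to 3499 (18 years and over) | 3500 or more (18 years and over) | none | No |
| Protein/creatinine ratio, under 18 years only | none | 0.5 to 1.9 | > 1.9 | none | No |

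The trial population is adult. That is stated in section 3.1 of SAP v2.0; the corresponding part of v3.0 is not shown. The ratio row therefore does not apply.

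**Step 2. Highest grade a qualitative result can receive.** Negative or ungraded = 0, + = 1, ++ = 2, +++ = 2. The maximum is max(0, 1, 2, 2) = 2. The grade-0 rule for missing grades cannot raise it.

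**Step 3. Count in the row.** The number at grade 3 or higher is the number of results with grade ≥ 3. Since no qualitative result exceeds 2, the count is 0 for any distribution of results.

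**Step 4. Illustration.** Assume 132 patients assessed at a visit, with the share at +++ varied and no one at ++. The number at Grade 2 or higher is 132 × share, rounded.

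| Share at +++ | 132 × share | Row at Grade ≥ 3 | Row at Grade ≥ 2 |
|---|---|---|---|
| 5% | 6.6 | 0 | 7 |
| 10% | 13.2 | 0 | 13 |
| 20% | 26.4 | 0 | 26 |
| 50% | 66.0 | 0 | 66 |
| 100% | 132.0 | 0 | 132 |

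The 132 is only a convenient denominator, borrowed from the evaluable number in section 3.3 of SAP v2.0. The shares are assumptions; the documents give none.

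**Step 5. Does another by-visit display fill the gap?** Of the displays in section 10.2, the by-visit values and changes omit urinalysis, the by-visit urinalysis shift table omits protein, and the graded shift table runs from baseline to worst grade rather than by visit. The grade 3 or higher row is the only by-visit summary of urine protein in that section.

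**The case against.** A reader might infer that the report will hide proteinuria and give false reassurance on renal risk. The documents do not support that.

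- The shift table from baseline to worst grade would show a negative-to-+++ patient as a move from Grade 0 to Grade 2, and the listings carry the results themselves.
- Renal activity is also captured by SLEDAI-2K (proteinuria, hematuria, pyuria, casts) and by BILAG (among others dipstick protein, protein/creatinine ratio, 24-hour protein, creatinine and active nephritis).
- Serum creatinine and eGFR are in the same grade 3 or higher table, and their scales reach Grade IV. Investigator-graded adverse events of grade 3 or higher are summarised separately.

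All of this stands. What remains lost is a by-visit count; the ++ and +++ results also share one grade wherever grades are used.

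A second tempting reading is that the row is certain to be zero in the trial. That goes too far. The sentence defining the table says protein without repeating that it is qualitative, Appendix 13.11 has an adult 24-hour row that reaches Grade III, and the BILAG worksheet has a 24-hour protein item. If graded 24-hour results are in the central laboratory data and are pooled under protein, the row could be non-zero. But section 10.2 does not list that test, so the text would still need correcting.

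It can also be said that no test, population or efficacy result depends on this row. That is true and limits the weight of the point. It does not make the row useful.

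**Conclusion.** The point holds in a limited form. Under section 10.2's own list and the grading in Appendix 13.11, the urine protein row of the by-visit grade 3 or higher table is zero in every arm at every visit and carries no information. The harm is one potentially misleading row and no usable by-visit count of urine protein; detection of proteinuria in the report as a whole is not at stake.

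The conclusion rests on two assumptions: patients are adults, and only the qualitative test feeds the row. If 24-hour protein also feeds it, the row can register events, but only from patients with that measurement, and the SAP does not say so. The point deserves correction before database lock because the cost is small.

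**What to change.** - For qualitative urine protein, tabulate patients at Grade 2 or higher (++ or +++) at each visit, with a footnote that Grade 3 cannot be reached on this scale.
- If 24-hour urine protein is in the central laboratory database, add it to the list in section 10.2 and tabulate it at grade 3 or higher against the mg/24h row of Appendix 13.11, as a row of its own.
- Do not derive grades from the protein/creatinine ratio. Appendix 13.11 grades the ratio only under 18 years and gives no conversion to a 24-hour amount.

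Simply dropping protein from the table would remove the misleading row but would leave section 10.2 with no by-visit summary of urine protein.

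The cost is a sentence in section 10.2, one table row and a footnote, using qualitative results already planned for reporting; the 24-hour row, if it applies, adds one more. Trial conduct and the primary analysis are untouched. The downside is that urine protein then has a different cut-off from the other parameters in the table, which the footnote must make plain.
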